Study treatments	
Test-Drug: Emodepside LSF oral solution (1 mg/mL) or matching placebo. Planned dose levels:
 
  
 Cohort	Dose level	Formulation	
   
 1	5 mg, OD, for 10 days	LSF oral solution (1 mg/mL)	
 
 2	10 mg, OD, for 10 days	LSF oral solution (1 mg/mL)	
 
 3	10 mg, BID, for 10 days (single dose on Day 9)	LSF oral solution (1 mg/mL)	
  
 
Emodepside administration will be given as fasted doses of LSF oral solution. Each morning dose will be given after an overnight fast of at least 9 h. On Days 0, 1, 8 and 9, subjects will fast until at least 4 h after dosing. On Days 2 to 7, subjects will fast until at least 1h after dosing. In Cohort 3, subjects will also fast for 2 h before and until 1 h after their evening dose.
 
Dose escalation will be decided by the Safety Review Group (SRG) at the Safety Review Meeting. The dose will not be escalated until the SRG have reviewed safety, tolerability and PK data until 48 h after the final dose of study medication in at least 4 subjects on active treatment (ie, at least 6 subjects overall), and agree that it is appropriate to give a higher dose; that decision will be taken in the Safety Review Meeting, before dosing of the subsequent cohort. The next planned dose level may be reduced, or a dose level may be re-tested or an intermediate dose level selected, based on emerging data.
 
The dose level will not exceed 20 mg LSF oral solution (1 mg/mL) per day.
 
If, within a treatment group, any of the following occurs, dose escalation will be stopped:
 
Safety stopping criteria
 
 There is 1 or more SAE, considered to be related to emodepside; 2 or more subjects in the same treatment group who present any severe or clinically significant AEs considered to be related to emodepside 
If a cohort fulfils a dose escalation stopping criterion, that dose level will not be repeated.
 
PK stopping criteria
 
 predicted mean plasma concentrations in the subjects at the next scheduled dose level exceed or equal: C_{max} 612 µg/L (based on the highest dose in the Single Ascending Dose (SAD) study DNDi-EMO-001)) 
The scheduled dose of emodepside may be reduced if, for example, the results of safety tests give any cause for concern, or tolerability is poor.
	Cohort	Dose level	Formulation	1	5 mg, OD, for 10 days	LSF oral solution (1 mg/mL)	2	10 mg, OD, for 10 days	LSF oral solution (1 mg/mL)	3	10 mg, BID, for 10 days (single dose on Day 9)	LSF oral solution (1 mg/mL)

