7.1. Doses and treatment regimens

Randomised subjects will be given a unique ID (subject number; Table 6) that will be recorded in the case report form (CRF), and will be retained throughout the study.

This subject number will also appear on the study medication containers.

Table 6 . Study treatment: Subject numbers, Formulation, and Dose-Levels by Cohort

	Subject numbers ^a	Formulation and route of administration	Planned subjects	
			Emodepside	Matching placebo
Cohort 1	1001 – 1008	5 mg LSF solution OD, or placebo, by mouth	6	2
Cohort 2	2001 – 2008	10 mg LSF solution OD, or placebo, by mouth	6	2
Cohort 3	3001 – 3008	10 mg LSF solution BID, or placebo, by mouth	6	2

^a Any subjects who are replaced in a cohort will have the subject number incremented by 100 (eg, 1001 would be replaced by 1101)

Subjects will receive the study medication according to fasting instructions given in Section 4.3: On dosing days, following an 9 h overnight fast (no food or drink, except water), Investigator site personnel will administer study medication (active or placebo) to subjects with 240 mL ambient temperature water.

Subjects in Cohort 3 will be given an evening dose approximately 12 h after their morning dose on Days 0–9: they'll fast for 2 h before and 1 h after that evening dose.

Study treatment will be administered under the supervision of Investigator site personnel, following site standard procedures to ensure treatment compliance.

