MRT _{last}	Mean Residence Time from time zero (pre-dose) to the time of last quantifiable concentration will be calculated using

$$MRT_t = \frac{AUMC_t}{AUC_t}$$

Where AUMC_t is the area under the first moment of the concentration-time curve from time zero (pre-dose) to the time of last quantifiable concentration

V_z/F Apparent volume of distribution will be calculated using the following formula:

$$V_z / F = \frac{Dose}{\lambda_z \bullet AUC_\infty}$$

Multiple Dose Day 9 parameters

λ_z	The terminal rate constant will be estimated by log-linear regression analysis on data points visually assessed to be on the terminal log-linear phase.
$t_{1/2}$	The terminal half-life will be calculated according to the following equation: $t_{1/2} = \ln 2 / \lambda_z$.
$t_{1/2,dom}$	The dominant half-life will be calculated from the terminal slope of the log concentration-time (0-24h) curve according to the following equation: $t_{1/2,dom} = \log_e 2 / \lambda_z$
AUC_{last}	The area under the concentration-time curve from time zero (pre-dose) to the time of last quantifiable concentration will be calculated using a trapezoidal method.
AUC_{last}/D	The area under the concentration-time curve from time zero (pre-dose) to the time of last quantifiable concentration, corrected for dose.
$AUC_{last,norm}$	The area under the concentration-time curve from time zero (pre-dose) to the time of last quantifiable concentration corrected by dose and body weight
AUC_{12}	Area under the plasma concentration-time curve during a 12 h dosing interval
AUC_{12}/D	Area under the plasma concentration-time curve during a 12 h dosing interval corrected for dose
$AUC_{12,norm}$	Area under the plasma concentration-time curve during a 12 h dosing interval corrected by dose and body weight
AUC_{24}	Area under the plasma concentration-time curve during a 24 h dosing interval
AUC_{24}/D	Area under the plasma concentration-time curve during a 24 h dosing interval corrected for dose
$AUC_{24,norm}$	Area under the plasma concentration-time curve during a 24 h dosing interval corrected by dose and body weight
AUC_{∞}	The area under the plasma drug concentration vs. time curve from time zero to infinity.
AUC_{∞}/D	The area under the plasma drug concentration vs. time curve from time zero to infinity, corrected for dose.
$AUC_{\infty,norm}$	The area under the concentration-time curve from time zero to infinity corrected by dose and body weight

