4.2.2 Secondary Endpoint(s)

Pharmacokinetic Variables:

Emodepside plasma concentration–time data will be used to derive the following PK parameters of emodepside:

- After the first dose of emodepside (Day 0):

- Main PK parameters:
- Cohorts 1 & 2: AUC_{24} , AUC_{24}/D , C_{max} , C_{max}/D
- Cohort 3: AUC_{12} , AUC_{12}/D , C_{max} , C_{max}/D
- After multiple doses of emodepside (Day 9):
 - Main PK parameters:
 - Cohorts 1 & 2: AUC_{∞} , AUC_{∞}/D , AUC_{24} , AUC_{24}/D , $C_{max,ss}$, $C_{max,ss}/D$
 - Cohort 3: AUC_{∞} , AUC_{∞}/D , AUC_{12} , AUC_{12}/D , $C_{max,ss}$, $C_{max,ss}/D$
- Accumulation ratios $RA(C_{max})$ and $RA(AUC_{tau})$ will be calculated
- C_{trough} will be derived from the concentration data (Days 1–9).

The above parameters may be calculated for the metabolites of emodepside, as appropriate.

Pharmacodynamic Variables:

- Time-matched profiles of glucose, glucagon, insulin, and cortisol
- Oral glucose tolerance test (OGTT)

Exploratory PK variables:

Emodepside plasma concentration–time data will be used to derive the following PK parameters of emodepside:

- After a single dose of emodepside (Day 0):
 - Cohorts 1 & 2: $AUC_{24,norm}$, $C_{max,norm}$, t_{max} , MRT_{last} , V_z/F
 - Cohorts 3: $AUC_{12,norm}$, $C_{max,norm}$, t_{max} , MRT_{last} , V_z/F
- After multiple doses of emodepside (Day 9):
 - $AUC_{\infty,norm}$, $AUC_{12,norm}$, $AUC_{24,norm}$, AUC_{last} , AUC_{last}/D , $AUC_{last,norm}$, $C_{max,ss,norm}$, $t_{1/2}$, λ_z , t_{max} , MRT_{∞} , V_z/F , CL_{ss}/F
 - Other optional parameters: AUC_{t-inf} , $\%AUC_{extra}$, points terminal

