3.1.2 Multiple Dose

Emodepside parameters to be calculated on Day 9.

Text Symbol	Definition	Calculation	Typical Units	Log Transform	WNL	CDISC Controlled Terminology	TFL Symbol
Concentrations during and after multiple dosing							
C_{trough}	Trough plasma concentration	Trough plasma concentration (measured concentration at the end of a dosing interval at steady state [taken directly before next administration]) obtained directly from the concentration-time data.	ng/mL	Y	-	CTROUGH	C_{trough}
Concentrations and times (after final dose)							
$C_{\text{max,ss}}$	Maximum (peak) plasma concentration at steady state	The maximum (peak) plasma concentration will be obtained directly from the concentration-time data.	ng/mL	Y	Cmax	CMAX	$C_{\text{max,ss}}$
$C_{\text{max,ss}}/\text{Dose}$	Dose-normalised C_{max} at steady state	The dose-normalised C_{max} will be calculated as $C_{\text{max}}/\text{Dose}$ administered	(ng/mL)/mg	Y	Cmax_D	CMAXD	$C_{\text{max,ss}}/D$
$C_{\text{max,ss,norm}}$	Observed maximum plasma concentration corrected by dose and body weight at steady state	The C_{max} normalised by dose and body weight will be calculated as $C_{\text{max}}/(\text{Dose administered} * \text{body weight})$	(ng/mL)/(mg*kg)	Y	-	CMAXWD	$C_{\text{max,ss,norm}}$
t_{max}	Time to reach maximum (peak) plasma concentration	The first time of maximum (peak) plasma concentration will be obtained directly from the concentration-time data.	h	N	Tmax	TMAX	t_{max}
Half-life (after final dose)							
λ_z	Terminal rate constant	The apparent terminal phase rate-constant (λ_z) will be estimated by linear regression of logarithmically transformed concentration versus time data.	1/h	Y	Lambda_z	LAMZ	λ_z
$t_{1/2}$	Terminal half-life	The terminal half-life calculated from the terminal slope of the log concentration-time curve, as follows: $t_{1/2} = \frac{\log_e 2}{\lambda_z}$	h	Y	HL_Lambda_z	LAMZHL	$t_{1/2}$
$t_{1/2,\text{dom}}$	Dominant half-life	The dominant half-life calculated from the terminal slope of the log concentration-time (0-24h) curve, as follows:	h	Y	HL_Lambda_z	LAMZHLD	$t_{1/2,0-24}$

Text Symbol	Definition	Calculation	Typical Units	Log Transform	WNL	CDISC Controlled Terminology	TFL Symbol
		$t_{1/2, dom} = \frac{\log_e 2}{\lambda_z}$					
Areas under the curve (after final dose)							

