AUC _{last}	Area under the plasma concentration-time curve from time zero to time of last measurable concentration	The area under the concentration-time curve from zero time (pre-dose) to the time of last quantifiable concentration will be calculated using the (specified) trapezoidal method.	h*ng/mL	Y	AUClast	AUCLST	AUC _{last}
AUC _{last} /Dose	Dose-normalised AUC from time zero to last measurable concentration	The dose-normalised AUC from time zero to last measurable concentration will be calculated as AUC _{last} /Dose Administered	(h*ng/mL)/mg	Y	-	AUCLSTD	AUC _{last} /D
AUC _{last,norm}	Area under the concentration-time curve from time zero to time of last measurable concentration corrected by dose and body weight	The AUC from time zero to last measurable concentration normalised by dose and body weight will be calculated as AUC _{last} /(Dose administered*body weight)	(h*ng/mL)/(mg*kg)	Y	-	AUCLSTWD	AUC _{last,norm}
AUC ₁₂ *	Area under the plasma concentration-time curve from time zero to time 12 h	The area under the concentration-time curve from zero time (pre-dose) to time 12 h will be calculated using the (specified) trapezoidal method. If λ_z is not estimable, a partial AUC is not calculated (when $t_{last} < t$).	h*ng/mL	Y	User specified area	AUCINT	AUC ₁₂
AUC ₁₂ /Dose *	Dose-normalised AUC from time zero to 12 h	The dose-normalised AUC from time zero to 12h will be calculated as AUC ₁₂ /Dose Administered	(h*ng/mL)/mg	Y	-	AUCINTD	AUC ₁₂ /D
AUC _{12,norm} *	Area under the concentration-time curve from time zero to 12h corrected by dose and body weight	The AUC from time zero to 12h normalised by dose and body weight will be calculated as AUC ₁₂ /(Dose administered*body weight)	(h*ng/mL)/(mg*kg)	Y	-	AUCINTWD	AUC _{12,norm}

Text Symbol	Definition	Calculation	Typical Units	Log Transform	WNL	CDISC Controlled Terminology	TFL Symbol
AUC ₂₄ **	Area under the plasma concentration-time curve from time zero to time 24 h	The area under the concentration-time curve from zero time (pre-dose) to time 24 h will be calculated using the (specified) trapezoidal method. If λ_2 is not estimable, a partial AUC is not calculated (when $t_{last} < t$).	h*ng/mL	Y	User specified area	AUCINT	AUC ₂₄
AUC ₂₄ /Dose **	Dose-normalised AUC from time zero to 24 h	The dose-normalised AUC from time zero to 24h will be calculated as AUC ₂₄ /Dose Administered	(h*ng/mL)/mg	Y	-	AUCINTD	AUC ₂₄ /D

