AUC _{24, norm} **	Area under the concentration-time curve from time zero to 24h corrected by dose and body weight	The AUC from time zero to 24h normalised by dose and body weight will be calculated as AUC ₂₄ /(Dose administered*body weight)	(h*ng/mL)/(mg*kg)	Y	-	AUCINTWD	AUC _{24, norm}

Text Symbol	Definition	Calculation	Typical Units	Log Transform	WNL	CDISC Controlled Terminology	TFL Symbol
AUC _∞	Area under the plasma concentration-time curve from time zero to infinity	The area under the concentration-time curve will be calculated using the (specified) trapezoidal method for the interval 0 to t _{last} (time t _{last} is the time at which the last non-zero level was recorded), plus the area under the exponential curve from t _{last} to infinity, calculated as follows: $AUC_{t-\infty} = \frac{\hat{C}_t}{\lambda_z}$ where \hat{C}_t is the predicted value of the concentration at t _{last} .	h*ng/mL	Y	AUCINF_pred	AUCIFP	AUC _{inf}
AUC _∞ /Dose	Dose-normalised AUC from time zero to infinity	The dose-normalised AUC from time zero to infinity will be calculated as AUC _∞ /Dose Administered	(h*ng/mL)/mg	Y	-	AUCIFPD	AUC _∞ /D
AUC _{∞,norm}	Area under the concentration-time curve from time zero to infinity corrected by dose and body weight	The AUC from time zero to infinity normalised by dose and body weight will be calculated as AUC _∞ /(Dose administered*body weight)	(h*ng/mL)/(mg*kg)	Y	-	AUCIFPWD	AUC _{∞,norm}
%AUC _{extrap}	Percentage of AUC _∞ extrapolated from from t _{last} to infinity	$\% AUC_{extrap} = \frac{100 \times AUC_{t-x}}{AUC_x}$	%	N	AUC_%EXTRAP_pred	AUCPEP	%AUC _{extrap}
Clearance, volume of distribution and mean residence time (after final dose)							
CL _{SS} /F	Apparent total clearance from plasma after oral administration	Apparent total clearance from plasma will be calculated using the following formula: $CL_{SS} / F = \frac{Dose}{AUC_t}$	L/h	Y	Clss_pred (actually derives Clss_F_pred for oral dose)	CLFTAU	CL _{SS} /F
V _z /F	Apparent volume of distribution after non-intravenous administration calculated at steady state	Apparent volume of distribution calculated at steady state will be calculated using the following formula: $V_z / F = \frac{Dose}{\lambda_z \cdot AUC_t}$	L	Y	Vz_pred (actually derives Vz_F_pred for oral dose)	VZFTAU	V _z /F

Text Symbol	Definition	Calculation	Typical Units	Log Transform	WNL	CDISC Controlled Terminology	TFL Symbol

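### Day 9 AUC∞/D and AUClast/D divide an area that contains carry-over from every earlier dose by what reads as one dose, so under linear kinetics 10 mg BID would show about 1.8 to 1.9 times the per-mg value of 10 mg OD

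*SAP*

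**What the plan says.** SAP Appendix B 3.1.2 puts the Day 9 areas under the heading "Areas under the curve (after final dose". They run from the Day 9 pre-dose sample to the last quantifiable concentration (AUClast) or to infinity (AUC∞). For the first, "The dose-normalised AUC from time zero to last measurable concentration will be calculated as" AUClast over *Dose Administered*. For the second, "The dose-normalised AUC from time zero to infinity will be calculated as" AUC∞ over the same divisor. The *norm* versions divide further by body weight. No subtraction of carry-over is described. *Dose Administered* is also the divisor for Cmax,ss/D, AUC12/D and AUC24/D, and it is not defined as single, daily or total dose.

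Protocol 8.4.2 defines AUC∞/D for Day 9 as "The area under the plasma drug concentration vs. time curve from time zero to infinity, corrected for dose", again without saying which dose.

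Protocol 2.2.3 and SAP 4.2.2 list AUC∞/D as a main Day 9 parameter for all three cohorts. AUClast/D is exploratory. AUC24/D is limited to Cohorts 1 and 2, and AUC12/D to Cohort 3.

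The regimens in the protocol summary are "10 mg, OD, for 10 days" for Cohort 2 and "10 mg, BID, for 10 days (single dose on Day 9") for Cohort 3.

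**The concern.** Area divided by dose measures exposure per mg in two settings: after a single dose taken to infinity, or over one dosing interval at steady state. The area from the last of many doses to infinity is neither. It holds the last dose's whole area plus the residue of every earlier dose. With a stated terminal half-life of 523 h and only nine days between first and last dose, most terminal-phase drug from the earlier doses is still present.

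Dividing by one dose therefore gives a number that grows with the dose count. Cohorts 2 and 3 are both divided by 10 mg although they have received different total amounts. AUC∞/D is the only main Day 9 dose-normalised AUC with the same name in the OD and BID cohorts, so a reader would naturally compare them on it. That reader would see nearly doubled exposure per mg where the kinetics had not changed.

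**Working it through.** The documents give no AUC/D figure to reproduce, so the check uses linear superposition of a single-dose curve built from the protocol's own figures.

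**Inputs**
- Cohort 2: one dose on each of Days 0 to 9, so 10 doses and 100 mg.
- Cohort 3: 9 × 2 + 1 = 19 doses and 190 mg, taking a single dose on Day 9 (protocol summary, Schedule of events footnote 8, section 8.3.8).
- Decline to 50, 25, 12.5 and 6.25% of Cmax at 3, 7, 16 and 47 h; terminal half-life 523 h; roughly dose-proportional exposure (protocol 1.4).
- Last PK sample on Day 30, that is (30 − 9) × 24 = 504 h after the Day 9 dose.

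**Bound that needs no fit.** If no drug were lost between doses, the area after the final dose would be proportional to the dose count, and the BID/OD ratio would be 19/10 = 1.90. Faster elimination pulls it towards 1.

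**Fitted curve (assumption).** C(t)/Cmax = Σ aᵢ·exp(−λᵢt), with times counted from the peak. The fit gives a = 0.8179, 0.1435 and 0.0387, with half-lives 2.31, 19.14 and 523 h (the last fixed).

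**Formula.** The area after the last of n doses at interval τ is Σ (aᵢ/λᵢ) × (1 − exp(−nλᵢτ)) / (1 − exp(−λᵢτ)). In hours, as multiples of single-dose Cmax:

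| Component | Single dose aᵢ/λᵢ | OD (n = 10, τ = 24 h) | BID (n = 19, τ = 12 h) |
|---|---|---|---|
| Fast | 2.7 | 2.7 | 2.8 |
| Middle | 4.0 | 6.8 | 11.2 |
| Terminal | 29.2 | 254.0 | 482.4 |
| Total | 35.9 | 263.5 | 496.4 |

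- **AUC∞/D ratio.** Both areas are divided by 10 mg, so BID/OD = 496.4/263.5 = 1.88.
- **AUClast/D ratio.** Multiplying each component by 1 − exp(−504λᵢ) gives 133.3 and 249.1, so BID/OD = 1.87.
- **Extrapolated share.** 1 − 133.3/263.5 = 49% for OD and 1 − 249.1/496.4 = 50% for BID. SAP Appendix B 1.2 bars use of AUC∞ above 40% unless justified.

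**Sensitivity (assumed ranges)**
- Times read from dosing with the peak at 1 h: 1.89 for both parameters, with 51% extrapolated.
- Terminal half-life from 75 to 523 h, or terminal coefficient cut to 0.5% of Cmax: AUC∞/D ratio 1.79 to 1.89, AUClast/D ratio 1.77 to 1.89.
- 20 doses in Cohort 3 instead of 19: AUC∞/D ratio 1.81 to 1.98.

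**The alternatives on the same curves**
- AUC12/D (BID) over AUC24/D (OD): 0.97 to 1.00.
- AUC∞ divided by total dose: (496.4/190)/(263.5/100) = 0.99 in the base case, 0.94 to 1.00 over all scenarios. For AUClast the range is 0.93 (1.77/1.90) to 0.99 (1.89/1.90).
- AUC∞ divided by daily dose (20 mg for BID): 0.90 to 0.95.

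**The case against.** **Not a planned comparison.** SAP 10 names active versus placebo as the comparison of interest. SAP 7.2 and 18.1 report Cohorts 1 and 2 separately from Cohort 3, in separate tables. SAP 4.3 leaves room for formal PK testing, but SAP 15 specifies only listings and descriptive summaries. The PK escalation rule uses predicted Cmax. This stands: a reader might infer that the flaw could produce a false dose-proportionality result or misdirect escalation, and the documents do not support that.

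**No distortion where cohorts share a table.** Cohorts 1 and 2 both receive ten OD doses, so the carry-over factor cancels. This stands. It would be wrong to say that every between-cohort reading of AUC∞/D is spoiled.

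**The extrapolation rule may remove AUC∞ anyway.** This is partly right. At 523 h about half the area is extrapolated, above the 40% limit, but with a shorter half-life or a smaller terminal coefficient the share can fall below it. AUClast/D has no such filter and carries the same distortion, though it is only exploratory.

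**The divisor is undefined.** If total dose were meant, the ratio would be near 1. But the same term divides Cmax,ss and AUC12, where only the individual dose makes sense, so one dose is the natural reading. If it is not the intended one, the SAP needs to say so.

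**An undistorted measure already exists.** AUC12/D and AUC24/D are main parameters. True, but under different names, which makes AUC∞/D the easier column to compare.

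It is also tempting to state how many times too high each Day 9 value is against single-dose AUC∞/D. In the base case the multiples are 263.5/35.9 = 7.3 (OD) and 496.4/35.9 = 13.8 (BID). They depend heavily on the assumed curve, the documents list no Day 0 AUC∞/D, and the one human AUC given (4,315 ng.h/mL at 40 mg) is of unstated type. The documents support only that the two quantities are not comparable.

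**Conclusion.** The point holds as a definition error in a listed main PK parameter and its exploratory companions. Followed as written, the Day 9 AUC∞/D and AUClast/D of 10 mg BID would be about 1.8 to 1.9 times those of 10 mg OD with no change in per-mg exposure. Neither value can be set against a single-dose AUC∞/D.

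The size rests on linear kinetics, on *Dose Administered* meaning one dose, and on 19 doses in Cohort 3. It depends little on the fitted curve. The consequence is limited to misreading of descriptive secondary PK results across regimens. The change is worth making because it is nearly free, but it does not threaten the primary safety objective or the 5 mg versus 10 mg OD comparison.

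**What to change.** In SAP 4.2.2 and Appendix B 3.1.2, and in protocol 2.2.3, 2.3 and 8.4.2:

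1. For Day 9, name AUCτ/D (AUC24/D for OD, AUC12/D for BID) and Cmax,ss/D as the dose-normalised parameters. Read AUCτ/D across regimens. Cmax,ss/D is a real peak, but accumulation alone puts its BID/OD ratio at about 1.3 to 1.4 on these curves.
2. Drop AUC∞/D, AUC∞,norm, AUClast/D and AUClast,norm for Day 9. Report the undivided area as *AUC from last dose*.
3. Alternatively, keep the four, define their divisor as total dose given, and label them accordingly. This brings the OD/BID ratio close to 1, but the area still leaves out exposure before Day 9, so the label must make clear that it is not a single-dose AUC/D.
4. Define *Dose Administered* wherever it remains.
5. Reconcile the Cohort 3 Day 9 dosing text, because it sets the dose count. Protocol 4.3 and 7.1 describe evening doses through Day 9, while the protocol summary, Schedule of events footnote 8 and section 8.3.8 describe a morning dose only.

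The cost is wording in two documents and up to four derived columns lost or relabelled. No sampling or data are affected.

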receiving placebo reported dry eye (n=1). All eye disorders AEs were of mild to moderate intensity, resolved spontaneously (without treatment), and were more frequently reported with highest dose (40 mg). Among them, the AEs of blurred vision, photophobia (“Increased ocular light sensitivity”), visual impairment (“distorted contrast perception”, “distorted colour perception”) reported by 8 out of 47 subjects receiving emodepside were considered as treatment-related by the Investigator. Also of note, at the highest dose (40 mg), lightheadedness (n=1), dizziness (n=1) or headache (n=1) were reported concomitantly to blurred vision.

None of the volunteers met any of the protocol-specified withdrawal criteria and overall tolerability to emodepside has been acceptable up to 20 mg. The presence of post-dose visual disturbances in subjects of Cohort 8 receiving either 40 mg solution or placebo may warrant some concern and escalation was stopped at this dose level.

The pharmacokinetic results obtained so far show that T_{max} for the LSF solution is consistently about 1 h post-dose when fasted. Mean C_{max} and AUC for the LSF solution have been roughly dose-proportional, with low to moderate inter-individual variability. The plasma half-life during the first 24 h is very short for a single dose of emodepside. After 3, 7, 16 and 47 h the maximum plasma concentration is reduced to 50%, 25%, 12.5% and 6.25% respectively. Terminal plasma half-life is 523 h. Although data of Cohort 9 (which was treated with a single dose of emodepside with food) are still under review, administration of the LSF of 10 mg with a high fat, high-calorie meal resulted in a clinically relevant food effect with a reduction of AUC to ~67%, C_{max} to 42% and a delay of the T_{max} up to 2.33 h. Therefore, the recommendation of administration of the emodepside (LSF) under fasted conditions is given.

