$\%AUC_{extrap}$	Percentage of AUC_{∞} extrapolated from from t_{last} to infinity, using the following formula
	$\%AUC_{extrap} = \frac{100 \times AUC_{t-\infty}}{AUC_{\infty}}$
$C_{max,ss}$	The observed maximum plasma concentration measured in a subject at steady state, identified by inspection of the drug concentration vs. time data.
$C_{max,ss}/D$	The observed maximum plasma concentration measured in a

	subject at steady state, identified by inspection of the drug concentration vs. time data, corrected for dose.
$C_{\max,ss,norm}$	The observed maximum plasma concentration at steady state, corrected by dose and body weight
t_{\max}	The time at which C_{\max} was apparent, identified by inspection of the drug concentration vs. time data.
MRT_{∞}	The mean residence time extrapolated to infinity
CL_{ss}/F	Apparent total clearance from plasma at steady state will be calculated using the following formula:

$$CL_{ss} / F = \frac{Dose}{AUC_{\infty}}$$

V_z/F	Apparent volume of distribution will be calculated at steady state using the following formula:
---------	---

$$V_z / F = \frac{Dose}{\lambda_z \bullet AUC_{\infty}}$$

$RA(C_{\max})$	Accumulation ratio for C_{\max} , calculated from C_{\max} at steady state and C_{\max} after single dose
$RA(AUC_{\tau})$	Accumulation ratio for AUC_{τ} , calculated from AUC_{τ} at steady state and AUC_t after single dose, where $t = \tau$.

Steady state (days 1 – 9)

C_{trough}	Trough plasma concentration (measured concentration at the end of a dosing interval at steady state [taken directly before next administration]) obtained directly from the concentration-time data.
---------------------	--

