1.2 AUC Calculations

The AUC will be calculated by a combination of linear and logarithmic methods. The linear trapezoidal method will be employed for all incremental trapezoids arising from increasing concentrations and the logarithmic trapezoidal method will be used for those arising from decreasing concentrations.

AUC_(0-∞) values with <20% of this area extrapolated will be reported.

It is acceptable to include data from profiles with >20% extrapolated as long as at least 80% of the profiles in the study have <20% of the AUC_(0-∞) as extrapolated area. In this instance, individual plasma concentration-time profiles for which the extrapolated areas are >20% of AUC_(0-∞) will be identified.

It is unacceptable to use AUC_(0-∞) data if >40% of the AUC has been extrapolated, except in specific situations which should be carefully justified in the study report.

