MRT _∞	Mean Residence Time extrapolated to infinity	The mean residence time will be calculated using: $MRT = \frac{AUMC}{AUC_{\infty}}$	h	Y	MRTINF_pred	MRTEVIFP	MRT _∞
Accumulation and time invariance ratios							
R _{ac} (AUC _t)	Accumulation ratio for AUC	Accumulation ratio will be calculated from AUC _t at steady state and AUC _t after single dose	-	N	-	ARAUC	R _{ac} (AUC _t)
R _{ac} (C _{max})	Accumulation ratio for C _{max}	Accumulation ratio will be calculated from C _{max} at steady state and C _{max} after single dose	-	N	-	ARCMAX	R _{ac} (C _{max})

* Calculated only for Cohort 3

**Calculated only for Cohorts 1 and 2

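### Day 9 mean residence time is computed as if the last dose were the only one, which overstates it by roughly 7–20% and leaves about 85% of AUMC extrapolated (exploratory parameter, low impact)

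*SAP*

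**What the plan says.** SAP Appendix B 3.1.2 has a block headed "Clearance, volume of distribution and mean residence time (after final dose"). Its MRT∞ row is defined as "Mean Residence Time extrapolated to infinity". The row then says "The mean residence time will be calculated using" AUMC/AUC∞, with MRTINF_pred as the software output. No term removes drug remaining from earlier doses. Protocol 8.4.2 names the same parameter ("The mean residence time extrapolated to infinity") and gives no formula.

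Both documents class it as exploratory: Protocol 2.3, and SAP 4.2.2 under "Exploratory PK variables".

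Other relevant text:

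- **Dosing.** The Protocol Summary's treatment table gives Cohort 1 as "5 mg, OD, for 10 days". Cohort 2 is also once daily and Cohort 3 twice daily.
- **Sampling.** The last PK sample is at Day 30 ± 2 days (footnote 12 of the schedule of events in both documents).
- **Single-dose kinetics.** Protocol 1.4 states "Terminal plasma half-life is 523 h". It also says the concentration falls to 50%, 25%, 12.5% and 6.25% of its maximum after 3, 7, 16 and 47 h, with Tmax about 1 h.
- **Extrapolation.** SAP Appendix B 1.2 calls AUC to infinity unacceptable "if >40% of the AUC has been extrapolated", unless specially justified. It mentions neither AUMC nor MRT.

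**The concern.** AUMC/AUC∞ is the average time a molecule of one dose spends in the body only if the profile starts from no drug. On Day 9 most of the drug under the curve came from earlier doses, and nearly all of that is in the slow phase. Clock zero is nevertheless reset to the last dose. The slow phase is therefore over-weighted, and the ratio drifts towards 1/λz whatever the residence time of a dose is.

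AUMC also weights late times most heavily, so it relies on the unobserved tail more than AUC does, yet no reporting limit applies to it. What is at stake is the meaning of one exploratory row: a figure labelled as residence time that is partly accumulation and mostly extrapolation.

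**Working it through.** Neither document states an MRT, an AUMC or a bias, so there is no figure of the plan's own to reproduce.

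**Inputs.** λz = ln 2/523 = 0.001325 per h, so 1/λz = 754.5 h. Decline points and Tmax are from Protocol 1.4. Doses: 10 at 24 h intervals in Cohorts 1 and 2. Cohort 3 has 9 × 2 + 1 = 19 at 12 h intervals, following the Protocol Summary, schedule footnote 8 and Protocol 8.3.8. Protocol 4.3 and 7.1 imply an evening dose on Day 9 as well; those passages must be reconciled. Linear superposition is assumed.

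**Method.** Fit C(t) = ΣAᵢ·exp(−λᵢt), in units of Cmax and with t from the peak, through the decline points with λ₃ = λz.

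- Single dose: MRT = Σ(Aᵢ/λᵢ²) / Σ(Aᵢ/λᵢ).
- Day 9 by the SAP formula: multiply each Aᵢ by Wᵢ = Σₖ exp(−λᵢkτ), k = 0 to n−1, and take the same ratio.

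For the terminal phase W is 8.70 (10 doses, 24 h) or 16.53 (19 doses, 12 h).

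**Reading 1: decline times run from the peak.** Coefficients 0.818, 0.143 and 0.0387; half-lives 2.31, 19.1 and 523 h.

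- Single dose: AUC 2.73 + 3.96 + 29.19 = 35.88; AUMC 9 + 109 + 22,022 = 22,140; MRT 617 h.
- 10 OD doses: W = 1.00, 1.72, 8.70; AUC 263.5; AUMC 191,843; ratio 728 h (+18%).
- 19 BID doses: W = 1.03, 2.84, 16.53; AUC 496.4; AUMC 364,308; ratio 734 h (+19%).

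**Reading 2: decline times run from dosing**, so 2, 6, 15 and 46 h after a 1 h peak. Coefficients 0.587, 0.348 and 0.0646; half-lives 1.06, 6.00 and 523 h.

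- Single dose: AUC 52.66; AUMC 36,806; MRT 699 h.
- 10 OD doses: AUC 428.3; AUMC 320,096; ratio 747 h (+7%).
- 19 BID doses: AUC 810.6; AUMC 607,933; ratio 750 h (+7%).

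Day 9 AUC∞ is thus about 7–8 times (OD) or 14–15 times (BID) that of one dose.

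**Other curve shapes through the same points.**

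| Curve | Single-dose MRT | OD | BID |
|---|---|---|---|
| Tri-exponential with 1 h rise, from peak | 610 h | 726 h (+19.2%) | 733 h (+20.2%) |
| Tri-exponential with 1 h rise, from dosing | 693 h | 747 h (+7.7%) | 749 h (+8.1%) |
| Piecewise log-linear, the two readings | 690 or 682 h | 746 or 745 h (+8.1% or +9.2%) | 749 or 748 h (+8.6% or +9.7%) |

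Moving the stated times by ±0.5 h gives mostly 7–9% (from dosing) or 8–18% (from the peak) for OD, with rare ill-conditioned fits far higher. Counting 20 doses in Cohort 3 changes its ratio by 1 h or less.

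**Ceiling.** The Day 9 ratio cannot exceed about 755 h, so the bias is capped near 754.5/617 = 1.22 (reading 1) or 754.5/699 = 1.08 (reading 2).

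**Extrapolation.** Day 30 is 21 × 24 = 504 h after the Day 9 dose, so x = 504 × 0.001325 = 0.668. For a pure exponential the AUC beyond 504 h is e⁻ˣ = 51% and the AUMC beyond it is (1 + x)e⁻ˣ = 1.668 × 0.513 = 85.5%. The fitted Day 9 curves give 49–51% and 85.4–85.5%. Over the ± 2 day window (456–552 h) the pure-exponential AUMC share runs from 88% to 83%.

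**The case against.** The strongest reply is that little hangs on this. MRT∞ is exploratory, there are six active subjects per cohort, and no escalation, stopping or interim rule uses it. The dose-escalation PK criterion is Cmax. All of that stands and sets the severity.

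The 40% rule is also a partial safeguard. With about half of AUC∞ extrapolated, the denominator would already need special justification, and the extrapolated percentage of AUC is itself a listed parameter. That stands too, but the rule says nothing about AUMC and does nothing about carry-over.

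The software might be run with a steady-state setting. The SAP does not say so and writes the uncorrected ratio. Nor would such a setting cure the problem: 240 h brings the terminal phase to only 1 − exp(−240λz) = 27% of steady state. The usual steady-state form, (AUMCτ + τ × AUC beyond τ)/AUCτ, gives 410–418 h against 617 h, or 578–584 h against 699 h.

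Stronger readings are tempting but not supported:

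- **A floor of 18%.** That figure needs the decline times to run from the peak. The protocol does not say which origin applies, and reading from dosing gives 7–10%.
- **Biases of 34–69%.** These come from halving or quartering the terminal coefficient. With the other terms of reading 1 unchanged, that puts the 47 h level at 4.4% or 3.5% of Cmax, against the stated 6.25%.
- **Much larger biases from a two-phase curve with an 11 h first phase.** Such a curve has AUC24/Cmax near 13 h. The stated decline gives about 6 h, and 4,315/612 = 7.05 h.
- **A distorted OD-versus-BID comparison.** The two ratios differ by about 1% or less.
- **The formula alone makes MRT restate the half-life.** The carry-over-free value is already 82–93% of 1/λz (617/754.5 to 699/754.5).

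**Conclusion.** The point holds, with low impact. Followed exactly, the SAP yields a Day 9 figure that is not the mean residence time of a dose. The bias was upward in every curve tested: roughly 7–20% on the protocol's single-dose decline points and 523 h half-life. Most of that range reflects the unstated origin of the decline times. About 85% of the numerator and about half of the denominator would be extrapolated.

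The size rests on linear superposition and on mean single-dose data described as preliminary. It depends on the share of single-dose AUC in the terminal phase, which the documents do not fix; a mono-exponential drug would show no such bias. The 4,315 ng·h/mL at 40 mg is taken as a truncated AUC, because reading 1 implies 35.88 × 612 ≈ 21,960 to infinity. No main PK, safety or dose-escalation result is affected through this parameter.

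**What to change.** Delete MRT∞ from the Day 9 non-compartmental parameters in Protocol 2.3 and 8.4.2 (and the matching Protocol Summary entry), SAP 4.2.2 and SAP Appendix B 3.1.2.

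If a residence time is wanted, derive it from a model fitted to each subject's whole multiple-dose profile with every dose included, as Σ(Aᵢ/λᵢ²)/Σ(Aᵢ/λᵢ) of the single-dose disposition. The model and estimation method would have to be specified, because SAP Appendix B 1.3 mentions compartmental analysis only conditionally. This removes the carry-over but not the dependence on the tail after Day 30, so report the extrapolated AUMC fraction beside it.

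The cost is one exploratory parameter lost, or one extra model fit. No new samples are needed.
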